5.2 Independent Data Monitoring Committee (IDMC)

This study will use an external IDMC to assess ongoing safety analyses in an unblinded manner. The committee will first meet to review the safety data from the study from a DCO approximately 12 months after the first patient has been dosed with IP or after approximately 50 patients have received at least 1 dose of IP (whichever occurs first). The frequency of subsequent reviews will be determined by the IDMC, but will be no more frequent than every 6 months.

This committee will be composed of therapeutic area experts, who are not employed by AstraZeneca and are free from conflict of interest.

Following the reviews, the IDMC will recommend whether the study should continue unchanged, be stopped, or be modified in any way based on the safety data that has been reviewed. Once the IDMC has reached a recommendation, a report will be provided to

AstraZeneca. The report will include the recommendation and any potential protocol amendments, and will not contain any unblinding information.

The final decision to modify or stop the study will sit with the sponsor. The sponsor or IDMC may call additional meetings if at any time there is concern about the safety of the study.

Full details of the IDMC procedures and processes can be found in the IDMC Charter (v17, 07 April 2022). The safety of all AstraZeneca/MedImmune clinical studies is closely monitored on an ongoing basis by AstraZeneca/MedImmune representatives in consultation with the Patient Safety Department. Issues identified will be addressed; this could involve, for instance, amendments to the Clinical Study Protocol and letters to Investigators.

Following the decision to stop recruitment, a decision was made on 21 November 2022 (during IDMC#1) to have no further IDMCs. A final safety report following DBL will be provided to the IDMC members.

6. CHANGES OF ANALYSIS FROM PROTOCOL

The following are changes from the planned analyses described in version 2 of the CSP.

Overall visit response table updated to more accurately reflect RECIST 1.1 evaluations and responses applicable to this study.

Except that change, this SAP has been produced in line with section 10.4 of CSP V2.0, which states:

“Under CSP v2.0, as a result of the decision by AstraZeneca to close enrollment to the study and end study assessments early, all analyses of the objectives and endpoints listed in Section 3 will be descriptive only and considered exploratory. Further details will be included in the SAP.”

8. APPENDICES

APPENDIX A Visit Windows

For example, the visit windows for vital signs data (with 4 weeks between scheduled assessments) are:

Day 29, visit window 2 - 42
Day 57, visit window 43 - 70
Day 85, visit window 71 - 98
Day 113, visit window 99 - 126
Day 141, visit window 127 - 154
Day 169, visit window 155 - 182
Day 197, visit window 183 - 210
Day 225, visit window 211 - 238
Day 253, visit window 239 - 266
Day 281, visit window 267 - 294
Day 309, visit window 295 - 322
Day 337, visit window 323 - 350
Day 365, visit window 351 - 378
Day 393, visit window 379 - 406
Day 421, visit window 407 - 434
Day 449, visit window 435 - 462
Day 477, visit window 463 - 490
Day 505, visit window 491 - 518
Day 533, visit window 519 - 546
Day 561, visit window 547 - 574
Day 589, visit window 575 - 602
Day 617, visit window 603 - 630
Day 645, visit window 631 - 658
Day 673, visit window 659 - 686
Day 701, visit window 687 - 714
Day 729, visit window 715 - 742

Note: The same rules should be followed if a patient has more than 26 cycles due to delayed durvalumab/placebo. Also, due to the differing assessment schedules the visit windows will be different for the different endpoints.

APPENDIX B Missing/Partial Dates Imputation

Imputation of partial date of birth

Patients with a partial date of birth will have an assumed date of birth of 1st January [given year]) for calculation of age at randomization.

Imputation of partial start/end dates for AEs and medications/therapies

In practice, for AEs and medications/therapies, original incomplete or missing start dates will be imputed as below:

- Missing day: impute the 1st of the month unless month is same as month of first dose of study treatment (i.e. durvalumab/placebo) then impute first dose date;
- Missing day and month: impute 1st January unless year is the same as year of first dose of study treatment (i.e. durvalumab/placebo) then impute first dose date;
- Completely missing: impute first dose date unless the end date suggests it could have started prior to this in which case impute the 1st January of the same year as the end date.

When imputing a start date, ensure that the new imputed date is sensible i.e. is prior to the end date of the AE or medication.

Original incomplete or missing stop dates for AEs and medications/therapies will be imputed as below:

- Missing day: impute as the earlier of either the DCO or the last day of the month unless month is the same as month of last dose of study treatment (i.e. durvalumab/placebo) then consider the last dose date;
- Missing day and month: impute as the earlier as either the DCO or 31st December unless year is the same as year of last dose of study treatment (i.e. durvalumab/placebo) then consider the last dose date;
- Completely missing:
 - AE: since there is no ongoing flag recorded in eCRF, then assume that AE is still present (i.e. do not impute a date);
 - Medication/therapy: if the ongoing flag is missing then assume that medication is still being taken (i.e. do not impute a date). If the medication has stopped and start date of medication is prior to first dose of study treatment (i.e. durvalumab/placebo) then impute as the day before the first dose date. If the medication has stopped and start date of medication is on or after first dose of study treatment (i.e. durvalumab/placebo) but before or on the last dose of study treatment (i.e.

durvalumab/placebo) then impute the earlier of either the DCO or the day after the last dose date.

When imputing a stop date, ensure that the new imputed date is sensible i.e. is after the start date of the AE or medication/therapy.

Duration of AEs or medications/therapies will not be derived using imputed dates.

Imputation of partial death dates

If a patient is known to have died where only a partial death date is available then the date of death will be imputed as the latest of the last date known to be alive + 1 day from the database and the imputed death date using the following:

- For missing day only – using the 1st of the month
- For missing day and month – using the 1st of January
- If there is evidence of death but the date is entirely missing, it will be treated as missing, i.e. censored at the last known alive date.

Imputation of partial start dates of subsequent anti-cancer therapy (including radiotherapy)

- For missing day only – using the 1st of the month
- For missing day and month – using the 1st of January

If the imputed start date for a subsequent anti-cancer therapy (including radiotherapy) results in a start date that is not after the date of last dose of study treatment (i.e. durvalumab/placebo), this will be flagged and discussed with the clinical team.

Other parameters

- No other imputation will be made.

SIGNATURE PAGE

This is a representation of an electronic record that was signed electronically and this page is the manifestation of the electronic signature

Document Name: d910mc00001-sap-ed-2		
Document Title:	Statistical Analysis Plan Edition 2	
Document ID:	Doc ID-004502317	
Version Label:	2.0 CURRENT LATEST APPROVED	
Server Date (dd-MMM-yyyy HH:mm 'UTC'Z)	Signed by	Meaning of Signature
23-Mar-2023 12:21 UTC	PPD [REDACTED]	Content Approval
22-Mar-2023 14:08 UTC	PPD [REDACTED]	Content Approval

Notes: (1) Document details as stored in ANGEL, an AstraZeneca document management system.

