Missing safety data will generally not be imputed. However, safety assessment values of the form of '< x' (i.e. below the lower limit of quantification) or '> x' (i.e. above the upper limit of quantification) will be imputed as 'x' in the calculation of summary statistics but displayed as '< x' or '> x' in the listings. Additionally, AEs that have missing causality (after data querying) will be assumed to be related to durvalumab or placebo.

For the handling of partial date of birth and missing/partial start and/or stop dates of AEs, medications/therapies, deaths and subsequent anti-cancer therapies (including radiotherapy), refer to Appendix B.

The original incomplete or missing dates will be presented in the listings.

All AEs will be considered as treatment-emergent unless the opposite can be clearly stated. Imputation will be done only in the context of identifying TEAEs.

All medications/therapies will be considered as concomitant unless the opposite can be clearly stated.

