4.2.11 Concomitant and Other Treatments

Information on any medications or therapies from first screening to 90 days after the last dose of study treatment (i.e. durvalumab/placebo) will be recorded in the eCRF. Thereafter, only subsequent regimens of anti-cancer therapy will be recorded in the eCRF.

Other anti-cancer therapies, investigational agents, and radiotherapy should not be given once the patient has completed curative intent therapy and while they are randomized and on study drug.

Medications received prior to, concomitantly, or post-study treatment will be coded using the World Health Organization drug dictionary (WHODD) Anatomical Therapeutic Chemical (ATC) classification codes. Concomitant medications/therapies will be summarized for the FAS by ATC classification codes.

For the purpose of inclusion in prior and/or concomitant medication or therapy summaries, incomplete medication or radiotherapy start and stop dates will be imputed as detailed in Section [4.1.2](#).

Prior, concomitant and post-study treatment medications and therapies are defined based on imputed start and stop dates as follows:

- Prior medications/therapies are those taken prior to study treatment with a stop date prior to the first dose of study treatment.
- Concomitant medications/therapies are those that started prior to study treatment and are ongoing at the first dose date of study treatment, or that started on or after the first dose date of study treatment but on or before the last dose date of study treatment.
- Post-study treatment medications/therapies are those with a start date after the last dose date of study treatment.

The following summaries will be produced for the FAS:

- Summary of allowed concomitant medications
- Summary of disallowed concomitant medications
- Summary of subsequent anti-cancer therapies (including radiotherapy)

All concomitant and other treatment data will be listed.

Missing coding terms should be listed and summarized as 'Not coded'.

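### A medication known to have stopped, begun before first dose and with no stop date at all is always classed as prior, against the SAP's own default of concomitant

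*SAP*

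**What the plan says.** Three parts of the SAP bear on this.

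- **Section 4.1.2, imputation rules**, sets the default: "All medications/therapies will be considered as concomitant unless the opposite can be clearly stated".
- **Appendix B, stop dates.** The branch in question opens "If the medication has stopped and start date of medication is prior to first dose of study treatment" and ends "then impute as the day before the first dose date". It applies only when the stop date is completely missing. The neighbouring branches behave differently. If the ongoing flag is missing, the drug is taken to be still in use and no date is imputed. If the drug has stopped but began during treatment, the stop becomes the data cut-off or the day following last dose, whichever comes first. For a partial date the rule is "Missing day: impute as the earlier of either the DCO or the last day of the month", with a parallel rule using 31 December when the month is missing too. Both partial-date rules turn to the last dose date when the known month or year matches that of the last dose.
- **Section 4.2.11** makes the imputed date decisive: "Prior, concomitant and post-study treatment medications and therapies are defined based on imputed start and stop dates as follows". It continues: "Prior medications/therapies are those taken prior to study treatment with a stop date prior to the first dose of study treatment". For a drug begun earlier, "Concomitant medications/therapies are those that started prior to study treatment and are ongoing at the first dose date of study treatment".

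Section 4.2.11 then plans FAS summaries of allowed and of disallowed concomitant medications. The SAP amendment history records that the imputation of completely missing medication end dates was revised in V2.0, so this is current text. No reason for the change is given.

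**The concern.** The imputation settles a question that the data leave open. A record saying that a drug began before first dose and has since stopped is compatible with a stop before treatment, during it or after it. Section 4.1.2 says what to do with that uncertainty: count the drug as concomitant. Appendix B does the reverse, and always in the same direction.

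At stake is the completeness of the two concomitant-medication tables. A drug that in fact overlapped with treatment, but whose stop date was never recorded, would not be counted there. Any error from this branch can only lower the counts.

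**Working it through.** The plan states no figure on this point. The check is to apply the rules to one record and vary only what is known about the stop.

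**Assumed dates for illustration:** drug started 1 February 2022, first dose 15 March 2022, data cut-off later than both.

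| What is known about the stop | Appendix B result | Class under 4.2.11 |
|---|---|---|
| Month and year only: March 2022 | 31 March 2022, or the cut-off if earlier, or the last dose date if last dose was that month | Concomitant |
| Year only: 2022 | 31 December 2022, or the cut-off if earlier, or the last dose date if last dose was that year | Concomitant |
| Stop date and ongoing flag both missing | No date; treated as still taken | Concomitant |
| Flagged as stopped, no date at all | 14 March 2022 | **Prior** |

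In the last row the true stop could lie anywhere from 1 February 2022 to the cut-off. So the record with no stop-date information beyond the fact of stopping receives the firmest non-concomitant answer. A record that at least places the stop in the year of first dose stays concomitant.

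**Is the result forced?** Yes. The imputed stop is the first dose date minus one day. That is before first dose, so the definition of prior is met, and the drug is not ongoing at first dose, so the definition of concomitant fails. No record entering this branch can come out otherwise.

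**Is the exception in 4.1.2 met?** Not by the conditions of the branch. They establish that the drug has stopped, not when, and neither document ties the ongoing flag to the patient's status on Day 1.

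**A side effect.** Appendix B also asks that an imputed stop fall after the start. A drug started on the day before first dose is given a stop equal to its start, which fails that check.

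**Size per patient.** SAP 1.2 expects about 30 randomized patients, allocated 1:1. Assuming an even split, 30 / 2 = 15 per arm, and one patient is 1 / 15 = 6.7 percentage points. This further assumes that the patient has no other medication counted in the same table row. The documents give no count of records with this pattern, so no expected total can be calculated.

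**The case against.** The case on the other side is mostly about reach, and much of it stands.

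- **The branch is narrow.** A reader might infer that any completely missing stop date is moved to before first dose. The text does not say so. Three conditions must hold together: the record is a medication or therapy rather than an adverse event, it is known to have stopped, and it began before first dose.
- **Not every such record would be concomitant under 4.1.2.** That section has an exception where the opposite is clear. Completed neoadjuvant or adjuvant therapy can meet it, because surveillance begins 8±1 weeks after adjuvant therapy or 12±1 weeks after surgery (Protocol 5.1.1, criterion 13).
- **It is tempting to conclude that prohibited drugs are being hidden.** The documents do not support that. Protocol 6.4.1 bars anti-cancer medication during surveillance, and exclusion criterion 15 bars concurrent cancer therapy. SAP 2.2 reports prohibited concomitant systemic anti-cancer therapy separately as an important deviation. Exclusion criterion 19 rules out non-exempt immunosuppressants within 14 days before first dose, so for an eligible patient prior is often the likelier truth for that class. Steroids begun on treatment for toxicity never enter this branch.
- **The records stay visible.** All concomitant and other treatment data are listed, and original incomplete or missing dates appear in the listings.
- **Reversing the rule has its own error.** Surveillance can last 96 weeks. A short course finished months before Day 1 and left without a stop date would be counted as concomitant, with the same 6.7-point movement per patient in the other direction.

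These points limit the consequence. They do not remove the contradiction. The branch is worded for medications and therapies without restriction, eligibility rules do not cover ordinary or exempt drugs, and listings do not correct a summary table. The last point is a real cost, but 4.1.2 has already chosen that direction.

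**Conclusion.** The inconsistency is real but narrow. For a medication or therapy that began before first dose, is known to have stopped and has a completely missing stop date, Appendix B combined with 4.2.11 always gives prior. Section 4.1.2 calls for concomitant unless the contrary is clear, and the partial-date and missing-flag branches do not share the forced result.

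The consequence is possible under-counting in the two FAS concomitant-medication summaries and nothing further. DFS and the adverse-event summaries do not use this stop date, and all analyses are descriptive and exploratory under CSP v2.0. The number of affected records is unknown and probably small. The 6.7 points illustrates one patient in an arm assumed to hold 15. A reader might take it as an expected bias, but the documents give no record count from which a bias could be estimated.

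**What to change.** In this branch of Appendix B, either impute no stop date or impute the first dose date. In both cases the drug is no longer stopped before first dose and counts as concomitant, as 4.1.2 intends. Imputing the first dose date also satisfies the requirement that the stop follow the start, and it does not stretch a short course across the treatment period. Appendix B already excludes imputed dates from duration, so only the classification changes.

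Keep the day-before-first-dose imputation only where other data clearly show that the drug had ended, such as completed neoadjuvant or adjuvant therapy, or a drug whose absence at Day 1 is documented by the eligibility check.

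The cost is one sentence in the SAP and the matching program change. The downside is that some truly prior drugs will be counted as concomitant. Querying the missing stop dates before database lock would reduce that number.

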#### **9.4.1.2 Primary endpoint: disease-free survival**

DFS is defined as the time from the date of randomization until the date of disease recurrence (local, regional, or distant disease recurrence or second primary NSCLC) using Investigator assessments according to RECIST 1.1, or date of death due to any cause, whichever occurs first.

Patients who are disease-free, ie, have not experienced disease recurrence, and alive at the time of analysis will be censored at the latest date of assessment from their last evaluable RECIST 1.1 assessment. However, if the patient experiences disease recurrence or dies after 2 or more missed visits, the patient will be censored at the latest evaluable RECIST 1.1 assessment prior to the 2 missed visits. If the patient has no evaluable assessments or does not have baseline data, they will be censored at Day 1 unless they die within 2 visits of baseline, then they will be treated as an event with the date of death as the event date. The primary endpoint analysis of DFS will be based on Investigator RECIST 1.1 assessments.

The DFS time will always be based on scan/assessment dates and not visit dates.

DFS rate at 6 and 12 months is defined as the proportion of patients alive and disease-free at 6 and 12 months respectively, estimated from Kaplan-Meier plots of the primary endpoint of DFS.

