#### **9.4.1.3 Secondary efficacy endpoint: overall survival**

OS is defined as the time from the date of randomization until death due to any cause. Any patient not known to have died at the time of analysis will be censored based on the last recorded date on which the patient was known to be alive.

**Note:** Survival calls (if agreed to by the patient and in compliance with local data privacy laws/practices) will be made following the date of DCO for the analysis (these contacts should generally occur within 7 days of the DCO). If patients are confirmed to be alive or if the death date is after the DCO date, these patients will be censored at the date of DCO. Death dates may be found by checking publicly available death registries.

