3.2 Efficacy Variables

3.2.1 Disease-Free Survival (DFS)

Disease-free survival as assessed by the Investigator is the primary endpoint in this study and is defined as the time from the date of randomization until any one of the following events below, whichever occurs first, regardless of whether the patient withdraws from randomized therapy or receives another anti-cancer therapy prior to disease recurrence (i.e., date of DFS event or censoring – date of randomization + 1 day):

- Date of disease recurrence using Investigator assessments according to RECIST 1.1
 - Local, regional, or distant disease recurrence
 - Diagnosis of a second primary NSCLC
- Date of death from any cause

Disease recurrence should be based on the finding of an unequivocal NL. However, if a NL is initially equivocal (i.e. where an equivocal lesion converts to unequivocal), then the progression date should be backdated to the post-baseline follow-up scan when the NL first appeared without an intervening period of lesion absence. If equivocal lesions are present at baseline, they will not be documented on the baseline eCRF.

Patients who have not experienced disease recurrence and are alive at the time of DCO will be censored at the latest date of assessment from their last evaluable RECIST 1.1 assessment.

However, if the patient experiences disease recurrence or dies after 2 or more missed visits, the patient will be censored at the latest evaluable RECIST 1.1 assessment prior to the 2 missed visits (note: an NE visit is not considered a missed visit). Given the scheduled visit assessment scheme (i.e. every 8 weeks \pm 1 week after randomization for the first 48 weeks, then every 12 weeks \pm 1 week thereafter until appearance of disease recurrence or until

primary DFS analysis) the definition of 2 missed visits will change. The definitions are shown in [Table 3](#).

Table 3 Definition of Two Missed Visits

Previous RECIST assessment	Two missed visits (duration)	Explanation
Study day < 274 (week 39)	18 weeks	$2 \times 8 \text{ weeks} + 1 \text{ week for an early assessment} + 1 \text{ week for a late assessment} = 18 \text{ weeks.}$
Study day 274 to < 344 (>week 39 to < week 49)	22 weeks	Over this period, the scheduled frequency of RECIST assessments changes from q8w to q12w. Take the average of 8 and 12 weeks which gives 10 weeks. $2 \times 10 \text{ weeks} + 1 \text{ week for an early assessment} + 1 \text{ week for a late assessment} = 22 \text{ weeks.}$

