4.2.2 Disease-Free Survival (DFS)

4.2.2.1 Primary Analysis of DFS

Disease-free survival, using Investigator assessment according to RECIST 1.1, will be summarized, for the FAS. This will include the number (%) of patients with event or censored, along with the reason for event/censoring. Kaplan-meier curves will also be produced.

DFS data on the PD-L1 $\geq 1\%$ analysis set will be listed only.

Supportive Summaries

Additionally, a summary of time to MRD+ emergence during surveillance may be provided and this may also be included in the DFS supportive listing.

The location of the disease recurrence (local/regional, distant or second primary NSCLC) will be summarized by treatment group.

Additionally, summary statistics will be presented for the number of days from censoring to DCO for all censored patients. A summary of the duration of follow-up will be summarized using time from randomization to date of censoring (date last known to have not had disease

recurrence or died) in censored patients only (patients who have not had disease recurrence or died), presented by treatment group.

A summary table of first subsequent cancer therapies relative to recurrence by treatment group will be provided.

All the collected RECIST 1.1 data will be listed.

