- AEs leading to discontinuation of study treatment
- AEs leading to discontinuation of study treatment, possibly related to study treatment (as determined by the reporting Investigator)
- AEs leading to dose interruption of study treatment

An overall summary of the number and percentage of patients in each category will be presented, as well as an overall summary of the number of episodes in each category. Summaries of the number and percentage of patients with AEs will be provided by maximum reported CTCAE grade, SOC, PT and treatment group. In addition, a truncated AE table of most common AEs and another table showing most common AEs with maximum CTCAE grade 3 or 4, showing all events that occur in at least 5% of patients overall will be summarized by PT, by decreasing frequency in the total column (the total column will not be displayed in the AE tables). This cut-off may be modified after review of the data. When applying a cut-off (i.e. $x\%$), the raw percentage should be compared to the cut-off, no rounding should be applied first (i.e. an AE with frequency of 4.9% will not appear if a cut-off is 5%).

In addition, all AEs will be listed (including listings for AEs that required treatment with steroids, immunosuppressants, or endocrine treatment, grade changes for AEs of CTCAE grade ≥ 3 , and grade changes for AEs of CTCAE grade ≥ 3 that required treatment with steroids, immunosuppressants, or endocrine treatment). Listings of key patient information for SAEs, and AEs leading to discontinuation of durvalumab/placebo or SoC will also be provided.

Deaths

A summary of all deaths will be provided with number and percentage of patients in the FAS by treatment group, categorized as:

- Total number of deaths (regardless of date of death)

- Death related to disease under investigation only, as determined by the Investigator
- Death related to disease under investigation and an SAE with outcome of death
 - (a) AE onset prior to subsequent anti-cancer therapy, defined as an AE with onset date (or pre-treatment AEs that increase in severity) on or after the date of first dose of study treatment and up to and including the earlier of 90 days following the date of last dose of study treatment or the date of initiation of the first subsequent anti-cancer therapy

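### SAP Appendix B censors a patient with evidence of death when the death date is entirely missing, in conflict with the protocol's OS rule and the SAP's general DFS rule

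*SAP*

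**What the plan says.** SAP Appendix B has two rules for incomplete death dates.

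- Partial date: "the date of death will be imputed as the latest of the last date known to be alive + 1 day from the database", compared with a date built from the known month or year. The death remains an event.
- No date at all: the rule for a patient with "evidence of death but the date is entirely missing, it will be treated as missing, i.e. censored at the last known alive date".

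The endpoint definitions describe whom to censor.

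- OS, protocol 9.4.1.3: "Any patient not known to have died at the time of analysis will be censored".
- DFS, protocol 9.4.1.2: "Patients who are disease-free, ie, have not experienced disease recurrence, and alive at the time of analysis will be censored at the latest date"; the date meant is that of the last evaluable RECIST assessment.
- DFS, SAP 3.2.1: "Patients who have not experienced disease recurrence and are alive at the time of DCO will be censored", again at the last evaluable RECIST assessment.

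SAP 3.2.1 also lists exceptions. A patient is censored at an earlier scan "if the patient experiences disease recurrence or dies after 2 or more missed visits". There are separate rules for patients with no evaluable assessment or no baseline data, and for patients with unequivocal disease at baseline.

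Under SAP v2.0, DFS in the FAS is the primary output. SAP 4.2.2.1 says of it: "This will include the number (%) of patients with event or censored, along with the reason for event/censoring", and adds Kaplan-Meier curves. OS is listed only (SAP 4.2.3). SAP 1.2 expects about 30 randomized patients.

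**The concern.** Death from any cause is a DFS event and the OS event. A patient with evidence of death is neither not known to have died nor alive at the cut-off, so the general censoring rules do not cover that patient, and an undated death is not one of the exceptions in SAP 3.2.1. Appendix B nevertheless makes the patient a censored observation.

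The rule also sits badly with the bullets above it. A death known only to the year is kept as an event, while a death with no date is turned into a non-event. Yet the last date known to be alive, which sets the earliest possible date in the first case, is available in the second as well. The DFS follow-up summary in SAP 4.2.2.1 describes censored patients as those without recurrence or death, and this patient would be placed among them.

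Censoring a patient when the evidence is that the patient died is informative, and it makes the arm look better. With about 15 patients per arm, a single misclassified death is visible in the retained primary output.

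**Working it through.** **The plan's own figures.** The documents give no figure for undated deaths. The superseded event targets do reproduce: 4 × (1.960 + 1.282)² / (ln HR)² gives 117.6, rounded up to 118, for HR 0.55, and 196.9, rounded up to 197, for HR 0.63. They have no bearing on this point.

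**Handling of a first event that is a death by the cut-off, with no recurrence recorded**

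| Death date | OS | DFS |
|---|---|---|
| Complete | Event | Event, unless a 3.2.1 exception applies |
| Partial (month or year known) | Event at imputed date | Event at imputed date, same exceptions |
| Entirely missing | Censored, last known alive | Not an event; Appendix B gives last known alive, 3.2.1 gives last evaluable RECIST assessment |

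The third row conflicts with protocol 9.4.1.3 for OS and with the general rule of SAP 3.2.1 for DFS. The two DFS censoring dates also differ, and the SAP does not say which prevails.

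**Crude proportion.** About 30 randomized 1:1 is about 15 per arm. One event recorded as censored moves that arm's event proportion by 1/15 = 6.7 percentage points, or 1/30 = 3.3 points of the whole FAS.

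**Kaplan-Meier, by hand.** Let n be the number at risk at the last known alive date, with k other events before the true death and no other censoring between. With the true date the curve is multiplied by (n − k − 1)/n; under Appendix B, by (n − k − 1)/(n − 1). From the death onwards the curve is therefore too high by the factor n/(n − 1). With exponential DFS and the protocol's placebo median of 4 months, 6-month DFS is 2^(−6/4) = 35.4%.

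- n = 15: 35.4% × 15/14 = 37.9%, up 2.5 points.
- n = 8: 35.4% × 8/7 = 40.4%, up 5.1 points.
- Death after 6 months: little or no change at 6 months.

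**Kaplan-Meier, by simulation.** 5,000 arms of 15, exponential with median 4 months. Assumptions not in the documents: administrative censoring uniform over 4 to 20 months, and last known alive 0 to 2 months before the event.

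| Undated deaths in the arm | 6-month DFS: true date | Appendix B | Last known alive + 1 day | Typical KM median, months (same order) |
|---|---|---|---|---|
| 1 | 35.0% | 37.6% | 34.7% | 4.0 / 4.3 / 3.9 |
| 2 | 34.9% | 40.3% | 34.2% | 3.9 / 4.5 / 3.8 |

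That is 37.6 − 35.0 = 2.6 points for one death, and (40.3 − 34.9)/2 = 2.7 points each for two. A second simulation used 4,000 two-arm trials per scenario, HR 0.63, follow-up uniform over 2 to 14 or 4 to 20 months, and the event censored at its own time. It gave mean rises of 3.0 to 4.2 points. Roughly 3 points summarises both.

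Both simulations recode a randomly chosen DFS event, because the documents do not split expected events into recurrences and deaths. The results are conditional on one DFS event being an undated death. They say nothing about how often that happens.

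**The case against.** Several stronger readings are tempting, and the documents do not support them.

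- **An undeclared breach of the protocol.** A reader might infer this because SAP Section 6 does not list the rule. But protocol 9.5 leaves procedures for missing data to the SAP, and the SAP amendment history records that the partial-death-date text was revised in v2.0. Silence in Section 6 is not the fault. What remains is that the rule conflicts with the endpoint definitions, one of them in the SAP itself.
- **A certain event is always discarded.** The bullet speaks of evidence of death. With no date, the record may not show that death fell by the cut-off, and protocol 9.4.1.3 censors at the cut-off a death dated after it. This stands, and it limits the fix.
- **No known death may ever be censored.** This fits the natural reading of the OS rule, but not DFS: both documents censor a death after two or more missed visits. A patient whose death is undated because contact was lost may well fall under that rule.
- **A distorted hazard ratio.** SAP v2.0 plans no Cox model and no hazard ratio. The affected outputs are the DFS counts and curve.
- **Undated deaths are likely after early closure.** The closing visits in protocol 10.2 are with the patient. The route through relatives or physicians in protocol 8.1.3 is marked as not applicable after v2.0. Protocol 8.3.4 and 8.3.11 provide for collecting the date of death for SAEs and for a Statement of Death page.
- **The deaths table will contradict the DFS table.** SAP 4.2.9.1 counts every death whatever its date, whereas DFS counts first events. The two differ by design, for example for deaths after recurrence.
- **Disease-free time is credited beyond the last scan.** That follows only if Appendix B overrides Section 3.2.1 for DFS, which the SAP does not state.

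The remaining argument is that a rare contingency in a closed, descriptive study of about 30 patients deserves no change. Rarity limits the expected effect, but it does not make the rule right.

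**Conclusion.** The concern holds within limits. Appendix B conflicts with the protocol's OS rule and with the general DFS rule, apart from the stated missed-visit, no-assessment and baseline-disease exceptions. Its DFS censoring date also differs from the last evaluable RECIST assessment.

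For DFS the effect arises only when death would be the first event and the missed-visit rule does not apply. For OS it changes a listing entry and no summary. The case is probably rare, and no frequency can be taken from the documents.

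If it occurs once in an arm of about 15, the crude event proportion shifts by 6.7 points, and 6-month Kaplan-Meier DFS rises by roughly 3 points, in that arm's favour. The second figure rests on the exponential and follow-up assumptions above. This is worth correcting before database lock because the primary DFS output is affected and the change is small; it does not threaten the study's conclusions, which are descriptive throughout.

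**What to change.** Replace the last death-date bullet in SAP Appendix B with:

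> If the evidence shows that the patient died on or before the DCO but the date is entirely missing, the death is counted as an event dated at the last date known to be alive + 1 day (not later than the DCO). For DFS, the Section 3.2.1 rules still apply, including censoring at the last evaluable RECIST assessment after two or more missed visits. Such dates are flagged in the listings, and the number of affected patients is reported by arm.

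Keep censoring where death by the DCO is not shown, with the DFS censoring date taken from Section 3.2.1.

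The cost is this bullet and a small programming change. The downside is that the imputed date is the earliest possible one, so time to death is slightly understated for that patient, as can already happen under the partial-date rule. An early date can also bring a death inside the missed-visit limit that its true date would have exceeded; the flag and the count by arm make this visible. In the simulation the proposed rule stayed within 1 point of the true-date result: 34.7% against 35.0% with one such death, and 34.2% against 34.9% with two.
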